#### 6.3.2.4.1 *Variable*

For analysis 2, the total nocturnal voiding volume will be derived as cumulative voiding volume between bedtime and waketime.

For analysis 3, the total nocturnal voiding volume will be derived as cumulative voiding volume between bedtime and wake time. Nights with 0 total nocturnal voiding volume will be set as missing.

# 6.3.2.4.2 Analysis

The total voiding volume per night will be averaged across voiding nights with available data (for baseline, Week 1, and Week 4 assessments). The mean total voiding volume and corresponding changes from baseline will be summarized descriptively by visit and treatment (based on all 3 approaches as described above). In addition, the total night voiding volume **plus** the morning volume will be summarized descriptively by visit and treatment (based on data derived by Minze Health).

Analyses will be repeated for the morning voiding volume and the total daytime voiding volume based on the data provided by Minze Health.

## 6.3.2.5 Change in number of nocturnal and daytime voids

Three analyses will be conducted for the number of nocturnal voids:

- 1. Number of nocturnal voids as derived by Minze Health (derived data are provided by Minze Health).
- 2. Derived number of nocturnal voids, defined as the number of nocturnal voids between bedtime and waketime.
- 3. Derived number of nocturnal voids, defined as the number of nocturnal voids between bedtime and waketime, excluding nights with 0 number of voids.

The rationale for the analysis is the same as described in Section 6.3.2.4.

# 6.3.2.5.1 *Variable*

For analysis 2, the number of nocturnal voids will be derived as the number of nocturnal voids between bedtime and waketime.

For analysis 3, the number of nocturnal voids will be derived as the number of nocturnal voids between bedtime and waketime. Nights with 0 voids will be set as missing.

Changes from baseline in the total number of nocturnal voids will be computed using averages across the 3 voiding nights ('Cycles') at baseline, Week 1, and Week 4 (based on available data in the corresponding treatment period).

# 6.3.2.5.2 Analysis

Changes from baseline to post-baseline visits in the number of nocturnal voids will be analyzed using an MMRM with treatment (daridorexant 50 mg; placebo), week within period (Week 1; Week 4), and period (TP I; TP II) as factors, baseline number of nocturnal voids as covariate, and the interaction of treatment and week. The MMRM will be applied to all 3 approaches, as described above.

An unstructured covariance matrix will be used to account for the correlation between repeated measurements from the same subject. A restricted maximum likelihood approach in combination with the Newton Raphson Algorithm will be used to derive (unbiased) estimates of variance components. The Kenward-Roger approximation will be used to compute the denominator degrees of freedom and adjust standard errors [Kenward 1997]. If the analysis fails to converge, the following structures will be tested in the subsequent order until model-convergence is achieved: heterogeneous Toeplitz, Toeplitz, autoregressive, and compound symmetry.

To evaluate the efficacy hypotheses, appropriate contrasts will be used to test the treatment differences of interest (i.e., the difference in LS Mean change from baseline to Week 4 between daridorexant 50 mg and placebo).

The LS Mean for each treatment per time point will be displayed with the associated standard errors and 95% CIs. For the comparison of daridorexant with placebo, the placebo-adjusted LS Mean will be displayed with the associated standard error, 95% CI and unadjusted 2-sided p-value.

The changes from baseline in the total number of nocturnal voids will be plotted over time (averaged across the 3 nights) by treatment (based on all 3 approaches).

The number of nocturnal voids and the change in the number of nocturnal voids will be analyzed descriptively, averaged across the 3 voiding nights, by treatment and visit (based on all 3 approaches).

Descriptive analyses will be repeated for the number of daytime voids, based on the data provided by Minze Health, by treatment and visit.

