3.4 Endpoints

It is anticipated that the collection of the voiding volume will interfere with sleep-related endpoints, therefore a staggered approach for the endpoint assessments is pursued. The details are described below and apply for each treatment period.

Information on the endpoints and their relation to the objectives is shown in Table 3.

Further details on the endpoints are described in the SAP.

Table 3Endpoints and objectives

Objectives	Endpoints in period I and period II			
To assess the efficacy of daridorexant on insomnia in subjects with insomnia and	Primary endpoint:Change from baseline to Week 4 in sTST			
comorbid nocturia	Other insomnia related endpoints:			
	• Changes from baseline to Week 1, Week 2, and Week 3 in sTST			
	• Changes from baseline to Week 2 and Week 4 in ISI [©] total score			
	• Changes from baseline to Week 1, Week 2, Week 3, and Week 4 in quality and depth of sleep as determined by scores on the VAS (mm) in the morning			
	• Changes from baseline to Week 1, Week 2, Week 3, and Week 4 in the daytime alertness and daily ability to function as determined by scores on the VAS (mm) in the evening			
	• Changes from baseline to Week 1, Week 2, Week 3, and Week 4 in mean number of self-reported awakenings based on the sleep diary			
To assess the efficacy of daridorexant on	Nocturia related:			
nocturia	• Changes from baseline to Week 1 and Week 4 in number of nocturnal voids assessed using a voiding diary			
	• Changes from baseline to Week 1 and Week 4 in the time to the first nocturnal void assessed using the voiding diary			
	• Changes from baseline to Week 1 and Week 4 in the volume of the first nocturnal void assessed using the voiding diary			
	• Changes from baseline to Week 1 and Week 4 in the total nighttime voiding volume assessed using the voiding diary			
	• Change from baseline to Week 1 and Week 4 in number of daytime voids assessed using a voiding diary			
	• Changes from baseline to Week 1 and Week 4 in the total daytime voiding volume assessed using the voiding diary			
	Change from baseline to Week 4 in ICIQ-NQoL			
	• Change from baseline to Week 4 in lower urinary tract symptoms sub-score using the ICIQ-MLUTS and FLUTS for male and female subjects, respectively			
To assess the overall patient's ratings of their condition and symptoms	• Changes from baseline to Week 1, Week 2, Week 3, and Week 4 in Patient Global Assessment of Disease Severity (daytime symptoms)			

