9.2.2.3 Analysis of primary estimand (primary efficacy analysis)

Changes from baseline to post-baseline visits in sTST will be analyzed using an MMRM with change from baseline in sTST as response, treatment group (daridorexant 50 mg; placebo), period (Period I; Period II), and week within period (Week 1; Week 2; Week 3; Week 4) as factors, baseline sTST assessment as covariate, and the interaction of treatment group × week.

To evaluate the efficacy hypotheses, the difference in LS mean change from baseline between daridorexant 50 mg and placebo at Week 4 will be estimated from the MMRM. An unstructured covariance matrix will be used to account for the correlation between repeated measurements from the same subject. In the event of convergence issues of the MMRM, the primary estimand will be estimated as described in the SAP. This approach relies on the Missing at Random assumption.

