# **6.3.1** Analysis of insomnia-related endpoints (ISI®, VAS, number of awakenings) All endpoints will be summarized based on the FAS.

# 6.3.1.1 Insomnia Severity Index©

The ISI© assesses the severity of a subject's insomnia by scoring the severity of sleep onset and sleep maintenance difficulties and any insomnia-related interference with daytime functioning. The assessment is on a 5-point scale (0–4) where the composite score is obtained by summing the 7 rated dimensions measuring the subject's perception of his or her insomnia. The ISI© will be completed by the subject on the eDiary at Visit 1 (baseline), Visit 3 (Week 2, Period 1), Visit 4 (Week 4, Period 1), Visit 7 (Week 2, Period 2), and Visit 8 (Week 4, Period 2).

The change from baseline to Week 2 and Week 4 will be summarized by treatment. Observed values will also be summarized. Changes from baseline to Week 2 and Week 4 will also be analyzed based on an MMRM, as described in Section 6.1.3.

In addition, the proportion of subjects with an ISI© decrease from baseline of greater than or equal to 6 will be summarized, as well as the proportion of subjects with ISI© values of 7 or less at Week 2 and Week 4, by treatment.

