## 13.2 SAS® code for mixed model for repeated measures

This model is used, for example, for the main analyses of the primary endpoint. Assuming the data are in 'long' format (i.e., one row for each subject/visit), example SAS® statements for the primary endpoint analysis are:

```
proc mixed data=data;
    class SUBJID TRT VIS PERIOD;
    model CHG = BASE TRT VIS PERIOD TRT*VIS / ddfm=kr;
    random int / subject=SUBJID;
    repeated VIS / subject=SUBJID*TRT type=un;
    lsmeans TRT*VIS / diff cl;
    estimate 'daridorexant 50 mg vs placebo at Week 4' TRT 1 -1 TRT*VIS 0 0 0 1 0 0 0 -1 / cl;

run;
```

The dataset 'data' includes baseline as well as changes (CHG) from baseline to Weeks 1, 2, 3, and 4 (VIS). Furthermore, TRT equals 1 and 2 for daridorexant 50 mg and placebo, respectively, and PERIOD equals 1 and 2 for TP I and TP II.

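### In the two-visit exploratory models (nocturnal voids, ISI) the covariance fallback list holds only one real alternative, and that one averages the Week 4 variance with the earlier visit's

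*SAP*

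**What the plan says.** SAP 6.3.2.5.2 fits the number of nocturnal voids with "week within period (Week 1; Week 4), and period (TP I; TP II) as factors". It starts from an unstructured matrix: "An unstructured covariance matrix will be used to account for the correlation between repeated measurements from the same subject". On non-convergence, "the following structures will be tested in the subsequent order until model-convergence is achieved: heterogeneous Toeplitz, Toeplitz, autoregressive, and compound symmetry". The same list stands in SAP 6.1.3 for the primary sTST model, which has four weekly visits.

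SAP 6.3.1.1 adds a second two-visit model, for ISI: "Changes from baseline to Week 2 and Week 4 will also be analyzed based on an MMRM, as described in Section 6.1.3". It takes over the 6.1.3 list by that reference.

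The only code, SAP 13.2, has a random subject intercept and the statement "repeated VIS / subject=SUBJID*TRT type=un". The structure therefore applies to the visits within one subject and one treatment. Protocol 9.2.2.3 leaves the matter to the SAP: "In the event of convergence issues of the MMRM, the primary estimand will be estimated as described in the SAP".

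In all these models the contrast of interest is daridorexant minus placebo at Week 4.

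**The concern.** A fallback list is useful only if each step is a simpler model than the one that failed. This list steps down through four weekly visits. Reused for two, it offers four names but one alternative, and that alternative forces the same variance at both visits.

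The result reported is at Week 4 only. If the variance of the within-subject difference is larger at Week 4 than at the earlier visit, an averaged variance makes the Week 4 interval too narrow; if smaller, too wide. The Kenward-Roger method corrects for small samples within the assumed structure. It does not repair a wrong structure.

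**Working it through.** **1. Parameter counts.** For t visits: unstructured t(t+1)/2, heterogeneous Toeplitz 2t−1, Toeplitz t, autoregressive 2, compound symmetry 2. The random intercept adds one variance to every row.

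| Structure | t = 2 | t = 4 |
|---|---|---|
| Unstructured | 3 | 10 |
| Heterogeneous Toeplitz | 3 | 7 |
| Toeplitz | 2 | 4 |
| Autoregressive | 2 | 2 |
| Compound symmetry | 2 | 2 |

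At t = 2 there is one off-diagonal element. Two variances and one correlation describe every 2×2 covariance matrix, so the first two rows are one family. One variance and one correlation is the common form of the other three.

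**2. Check by fitting.** The SAP 13.2 model was fitted by REML to simulated 50-subject cross-over data.

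| Data | Structures | −2 restricted log-likelihood | Week 4 SE |
|---|---|---|---|
| Complete | Unstructured, heterogeneous Toeplitz | 50.147 | 0.1403 |
| Complete | Toeplitz, autoregressive, compound symmetry | 67.134 | 0.1131 |
| With missing values | Unstructured, heterogeneous Toeplitz | 66.244 | 0.1519 |
| With missing values | Toeplitz, autoregressive, compound symmetry | 74.057 | 0.1298 |

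Within each group the fitted matrices were identical. In 75 further data sets a simple Newton-Raphson routine failed for unstructured in 2, and heterogeneous Toeplitz failed in the same 2.

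**3. Size of the error, two visits.** The documents give no variance by week, so the ratio r of the Week 4 to the earlier variance of the within-subject difference is an assumption. With complete data the subject intercept cancels from the difference. The equal-variance SE divided by the correct SE is then, in large samples, k = √[(1+r)/(2r)], and the actual level is P(|Z| > 1.96k). The simulations used 50 subjects in two sequences of 25, with the period effect removed.

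| r | k | Level by formula | Level by simulation |
|---|---|---|---|
| 2/3 | 1.118 | 2.8% | 2.7–3.1% |
| 1 | 1 | 5% | about 5% |
| 1.25 | 0.949 | 6.3% | 6.0–6.3% |
| 1.5 | 0.913 | 7.4% | 6.8–7.0% |
| 2 | 0.866 | 9.0% | 8.1–8.6% |

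A test that used only the Week 4 variance held 4.8–5.3%.

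**4. On the scale of voids.** Protocol 9.4.1 considers SDs of the within-subject difference of 0.7, 1.0 and 1.2, without assigning them to weeks. As an illustration, take 0.7 at Week 1 and 1.0 at Week 4. The correct SE is 1.0/√50 = 0.141. The averaged one is √[(0.49+1.00)/2]/√50 = 0.122. With the SDs reversed, the correct SE is 0.099 against the same 0.122.

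**5. Four visits.** The counts 10, 7, 4, 2, 2 show a real descent, but the last three steps hold one variance for all weeks. If that variance is the mean over weeks and the true variance rises linearly, Week 4 to Week 1 ratios of 1.5, 2 and 3 gave simulated levels of about 7.0%, 8.6% and 10.5%. If only Weeks 1 and 4 carry 30–60% more variance, compound symmetry gives about 6.3–7.7%. Autoregressive and Toeplitz structures, which come earlier in the list, give about 5.6–6.6% under serial correlation of 0.7–0.85.

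**The case against.** Four objections have force.

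- **The averaging is two failures away.** A reader might infer that any failed unstructured fit gives a Week 4 standard error averaged over weeks. The SAP does not say that. Heterogeneous Toeplitz is tried next and keeps a separate Week 4 variance. As a different parameterisation it may converge in software where the unstructured form does not, and its Week 4 SE is then the unstructured one. Both must fail, and with a 2×2 block and about 50 subjects that should be uncommon. This stands.

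- **The urine-collection schedule does not make the variances unequal here.** Protocol 3.4 says "It is anticipated that the collection of the voiding volume will interfere with sleep-related endpoints", and collection falls in Weeks 1 and 4 but not in Weeks 2 and 3. It is tempting to infer unequal variances from that. For voids, however, the two visits are Weeks 1 and 4, each with three collection nights. For ISI, the two-week recall at Weeks 2 and 4 covers one three-night collection each time under the nominal schedule (Days 2–4 and 26–28). The argument bears only on sTST, and even there the protocol speaks of interference, not of variance.

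- **The primary list is not broken.** With four visits it is an ordered, pre-specified descent. What remains is narrower: its last three steps do not keep a Week 4 variance.

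- **Another reading of the model exists.** If the structure were meant for a 4×4 matrix of period by week, the five structures would differ even with two visits. No code in the SAP supports that reading.

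Voids and ISI are also exploratory endpoints; the voids p-value is labelled unadjusted. The algebra is not in dispute.

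**Conclusion.** The point holds as a minor defect in the SAP. For nocturnal voids and ISI, under the SAP 13.2 block, the four-step list contains one real alternative. If it is reached, the Week 4 inference uses a variance averaged over two visits. A nominal 5% test then runs at about 6 to 8.6% for assumed variance ratios of 1.25 to 2, and at about 3% for a ratio of two thirds. If the variances are equal, or if either of the first two structures converges, nothing changes. The probability of reaching the fallback cannot be derived from the documents.

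For sTST only the weaker statement holds, that the late steps impose one variance on all weeks while the test is at Week 4. The four-visit figures depend on the assumed pattern over weeks and, in part, on using the mean weekly variance in place of a full model fit. The issue matters most for the sex and country analyses in SAP 6.1.8 if these are fitted separately. SAP 2 names three countries and SAP 6.3.3.3.1 says that the study is mainly in one of them, so some subsets may be small for a 10-parameter matrix. The SAP does not say whether the fits are separate.

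**What to change.** - **SAP 6.3.2.5.2 (voids) and 6.3.1.1 (ISI):** after unstructured and heterogeneous Toeplitz, go directly to the period-adjusted t-test on each subject's Week 4 daridorexant-minus-placebo difference. The estimate is the mean of the two sequence means, with 25 + 25 − 2 = 48 degrees of freedom if all 50 subjects contribute. Heterogeneous autoregressive or compound symmetry would not help here: two variances and one correlation are again the unstructured matrix. ISI needs its own sentence because it now inherits 6.1.3.
- **SAP 6.1.3 (sTST):** replace the three homogeneous structures by heterogeneous autoregressive and heterogeneous compound symmetry (four variances and one correlation each), with the same t-test as the last step. The VAS and IDSIQ models follow by reference.

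The t-test needs no model for the covariance between weeks and uses only the Week 4 variance. It is close to the paired t-test behind the sample size. Both periods share one pre-treatment baseline, so the baseline cancels from the difference.

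The cost is SAP wording; Protocol 9.2.2.3 already defers to the SAP. The statistical price is that the last step drops subjects without Week 4 data in both periods. For sTST the plan expects dropout below 3%. For voids the loss may be larger, because only completed cycles count and analysis 3 sets nights without voids to missing.

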# 6.3.3 Quality of life and treatment preference endpoints

All analyses will be conducted based on the FAS.

Page 29/50

Statistical Analysis Plan for Clinical Study Report Version 2 Doc No D-24.149

# 6.3.3.1 ICIQ-MLUTS and ICIQ-FLUTS

The ICIQ-MLUTS is a questionnaire that evaluates lower urinary tract symptoms in males. It is a patient-completed questionnaire that includes 13 items. It is split into two subscales ranging from 0–20 for voiding symptoms and 0–24 for incontinence symptoms, where higher numbers indicate a higher burden. It will be completed by the subjects on the eDiary at Visit 1, Visit 4, and Visit 8.

The ICIQ-FLUTS is a questionnaire that evaluates lower urinary tract symptoms in females. It is a patient-completed questionnaire that includes 12 items. It is split into 3 subscales ranging from 0–16 for filling symptoms, 0–12 for voiding symptoms, and 0–20 for incontinence symptoms, where higher numbers indicate a higher burden. It will be completed by the subjects on the eDiary at Visit 1, Visit 4, and Visit 8.

#### 6.3.3.1.1 Variable

For the ICIQ-MLUTS voiding symptoms score, the items of questions 2a–6a will be summed. For the ICIQ-MLUTS incontinence symptoms score, the items of questions 7a–12a will be summed. Answers to questions 2b–12b will not be analyzed.

For the ICIQ-FLUTS filling symptoms score, the items of questions 2a–5a will be summed. For the ICIQ-FLUTS voiding symptoms score, the items of questions 6a–8a will be summed. For the ICIQ-FLUTS incontinence symptoms score, the items of questions 9a–13a will be summed. Answers to questions 2b–13b will not be analyzed.

Changes from baseline (Visit 1) will be calculated for each sub-score, separately for men and women.

#### 6.3.3.1.2 Analysis

The change from baseline to Week 4 for all sub-scores of ICIQ-MLUTS and ICIQ-FLUTS will be summarized by treatment and sex. Observed values will also be summarized.

## 6.3.3.2 ICIQ-NQoL

The ICIQ-NQoL is a subject-completed questionnaire covering daytime and nighttime impact of nocturia in men and women, and consists of 13 items. The recall period is 4 weeks. The overall score is calculated by summing the first 12 items (ranging from 0–4), resulting in an overall score that ranges from 0–48, where greater scores indicate a greater decrease in quality of life. It will be completed by the subjects on the eDiary at Visit 1, Visit 4, and Visit 8.

#### 6.3.3.2.1 Variable

All items of questions 3–14 will be summed for one overall score. Changes from baseline will be calculated.

#### 6.3.3.2.2 *Analysis*

The change from baseline to Week 4 for the overall ICIQ-NQoL score will be summarized by treatment. Observed values will also be summarized.

